(i.e., impaired motor and sensory mechanisms of swallowing) or decreased level of consciousness leading to impaired cough reflex and glottic closure. Moreover, prophylactic antibiotic use in acute stroke patients does not reduce the incidence of post-stroke pneumonia or improve outcomes^[12,13].

Dysphagia is a common symptom in terminal illnesses. In the last weeks to months of life, declining swallowing function diminishes the desire and ability to eat. Difficulty swallowing solids and liquids is one of the most common symptoms in the final days of life^[13,14]. Swallowing disorders affect quality of life (e.g., social interaction, communication) and lead to impaired nutrition and hydration. Dysphagia is also a major predisposing condition for aspiration and can lead to pneumonia, and in some cases, even choking or death.

Considering the central role of food and nutrition in social interaction and the general concern about nutrition for health, swallowing disorders can also cause frustration and distress for family caregivers and healthcare staff.

Additionally, for many patients with terminal illnesses, the inability to swallow and/or lack of interest in food can be a critical symptom prompting decisions to forgo treatment and seek end-of-life care. Dysphagia refers to difficulty swallowing food or liquids, including medications in liquid or pill form. Post-stroke dysphagia (Post-Stroke Dysphagia, PSD) may arise from motor or sensory dysfunction in neurological processes, potentially causing problems with eating certain types of food or liquids, or even an inability to swallow altogether. Patients may complain of food sticking in the upper

gastrointestinal tract from the throat to the distal esophagus, and experience coughing or choking when eating or drinking. Chronic dysphagia affects the efficiency of oral intake, leading to physical weakness, loss of appetite, weight loss, dehydration, and malnutrition. Furthermore, airway protection or swallowing safety can be threatened by swallowing disorders. Food or liquid may enter the trachea, leading to aspiration, choking, or in severe cases, asphyxiation. Aspiration pneumonia is an infectious process caused by the aspiration of oropharyngeal secretions colonized by pathogenic bacteria, with Gram-negative enteric bacilli and anaerobes being the most common causative microorganisms. Aspiration of sterile acidic gastric contents can also cause acute chemical injury to the lungs.

Therefore, improving post-stroke dysphagia is particularly important for treating SAP, as it addresses the underlying cause, significantly reduces the incidence of SAP, and improves outcomes. Swallowing is not a voluntary act but a complex reflex that requires specific stimuli to initiate. Although the swallowing action can be started voluntarily, its completion is a complex reflex. A single simple swallow requires the coordination of 25 pairs of muscles in the oral cavity, pharynx, larynx, esophagus, and face, involving at least 6 pairs of cranial nerves, the speech system, and the respiratory system. Swallowing is a typical, complex reflex action consisting of a sequence of interlinked stages, each composed of a series of processes, where the activity of one stage can trigger the next. Receptors for swallowing are located in the

soft palate, posterior pharyngeal wall, epiglottis, esophagus, etc. Afferent nerves include fibers from the soft palate (Cranial Nerves V, IX), posterior pharyngeal wall (CN IX), epiglottis (CN X), and esophagus (CN X). The central pattern generator is located in the medulla oblongata. Efferent nerves are in Cranial Nerves V, IX, X, XI, and XII, and the effector organs include the tongue, larynx, pharyngeal muscles, esophageal muscle groups, etc. Every stage of swallowing is interconnected and indispensable. After a stroke, if the lesion involves the medulla oblongata, swallowing and breathing difficulties can occur.

Domestic research has primarily focused on the prevention of SAP-related risk factors, bundled care, rehabilitation training, and traditional Chinese medicine acupuncture, with a lack of reports on bronchoscopy for treating post-stroke dysphagia. Bedside bronchoscopy can clear airway secretions, pass directly through the glottis, stimulate cough and swallowing muscles to produce contractions, playing a positive role in preventing aspiration and alleviating dysphagia. Bronchoscopy can directly stimulate the trigeminal nerve in the soft palate, the glossopharyngeal nerve in the posterior pharyngeal wall, and the vagus nerve in the epiglottis, promoting contraction of the masticatory muscles, suprathyroid muscles, infrathyroid muscles, facial muscles, tongue muscles, and soft palate muscles, thereby training the swallowing muscle groups, exercising swallowing function, improving swallowing disorders, and significantly reducing the incidence and mortality rate of SAP.

Currently, there are no reports domestically or internationally on bedside bronchoscopy for the treatment of post-stroke dysphagia and SAP. This study aims to explore the application value and clinical safety of portable fiber bronchoscopy in non-severe SAP patients with dysphagia, and to evaluate whether bronchoscopic treatment can alleviate dysphagia symptoms, improve hypoxia, pulmonary infection, and SAP prognosis.

II. Study Objectives

Primary Objective: To observe the efficacy of bronchoscopic sputum suction + lavage therapy on post-stroke dysphagia and stroke-associated pneumonia.

Secondary Objectives: To compare National Institutes of Health Stroke Scale(NIHSS scores)(It is a standardized tool used to assess the degree of neurological deficits in patients with acute stroke, consisting of 15 items covering consciousness level, visual field, facial paralysis, limb movement, ataxia, sensory, language, and articulation disorders. The scoring range for each project is 0 to 4 points, with 0 indicating no defects and higher scores indicating more severe neurological deficits; The total score ranges from 0 to 42 points, with 0 indicating no neurological deficits and 42 indicating extremely severe deficits), Acute Physiology and Chronic Health Evaluation (APACHE) II scores(It includes three parts: acute physiology score (APS), chronic physiology score (CPS), and patient age score, with a total score of 0-

71 points. The higher the score, the more severe the patient's condition, the worse the prognosis, and the higher the mortality rate), CPIS scores (Clinical Pulmonary Infection Scores), Water Swallow Test scores(Grade I: able to drink without coughing within 5 seconds; Grade II: No coughing after drinking twice or more; Grade III: Can be consumed in one go but accompanied by coughing; Grade IV: Drink twice or more with coughing; Grade V: Frequent coughing and inability to finish all drinks. Grade I indicates normal, Grade II indicates suspicious, and Grade III or above indicates abnormal), C-reactive protein (CRP), Length of hospital stay, arterial partial pressure of oxygen (PaO_2), Height(m), Weight(Kg),Body Mass Index (BMI, Report BMI in kg/m^2 by combining weight and height) ,and overall clinical treatment efficacy between the two groups.

III. Study Plan

1. Study Population Selection

This is a single-center, prospective, randomized, controlled clinical trial. The control group will receive conventional anti-infective and expectorant therapy, plus suction via suction catheter as needed (i.e., when dyspneic or when phlegm sounds are heard in the airway). The observation group will receive, in addition to the control group's treatment, bronchoscopic treatment 1-2 times, including sputum suction under endoscopy, lavage, and drug

instillation. This study will enroll 60 patients with post-stroke dysphagia and stroke-associated pneumonia, randomly divided into an experimental group and a control group.

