1.1 Inclusion Criteria

- Meets the diagnostic criteria for acute stroke and is clearly diagnosed through head MRI or CT examination.
- According to the Wada drinking water test, there is indeed difficulty swallowing.
- Pneumonia occurs within 72 hours after stroke, confirmed by chest imaging examination, and meets the diagnostic criteria for stroke-related pneumonia.
- Clear consciousness, stable vital signs, and able to cooperate with bronchial examination.

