5.3 Research Methods

The control group will receive conventional anti-infective and expectorant therapy, plus suction via suction catheter as needed (i.e., when dyspneic or when phlegm sounds are heard in the airway). The observation group will receive, in addition to the control group's treatment, bronchoscopic treatment 1-2 times, including sputum suction under endoscopy, lavage, and drug instillation. Specific procedure steps: Prepare for the bronchoscopy procedure. Under continuous nasal cannula oxygen and vital sign monitoring via ECG, administer Atropine Injection 0.5mg (National Drug Approval No. H37021468, Shandong Huixin Pharmaceutical Group Co., Ltd.) combined with Lidocaine Injection (National Drug Approval No. H20065387, China Otsuka Pharmaceutical Co., Ltd.) 0.1g via nebulization for local anesthesia. Insert the Olympus BF-P180 fiber bronchoscope routinely through the nostril, sequentially entering various levels of bronchi. Under direct vision, clear airway secretions, collect lavage fluid for bacterial culture and drug sensitivity testing. If sputum is thick and difficult to suction, lavage with normal saline

can be used. Simultaneously, select sensitive antibiotics for instillation therapy based on the bacterial culture results of the airway secretions. After completion, slowly withdraw the bronchoscope. Both groups will receive continuous treatment for 1 week. Throughout the process, closely monitor the patient's vital signs. If oxygen saturation falls below 80% or heart rate exceeds 130 beats/min, immediately withdraw the fiber bronchoscope and provide symptomatic treatment. Resume the subsequent procedure after vital signs stabilize.

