[Moderate] The adverse event causes discomfort to the subject and interferes with the subject's normal activities.

[Severe] The adverse event significantly affects the subject's daily activities, may cause incapacitation, or is life-threatening.

3. Reporting of Serious Adverse Events

In the event of a Serious Adverse Event, regardless of whether it is related to the device or the control device, the physician must notify Olympus (China) Co., Ltd. within 24 hours of becoming aware of the event.

V. Ethics and Quality

Ethics committee approval will be obtained prior to the initiation of this study.

Before enrolling a patient, authorization must be obtained for the use and/or disclosure of personal and/or health data. To protect patient privacy, the patient's age will be recorded on the Case Report Form instead of the date of birth, and the patient's initials will be recorded on the Case Report Form.

The consistency of the collected Case Report Form data will be checked. Data queries will be issued for inconsistent data, requiring clarification by the physician.

VI. Data Management

Investigators must fill in the collected data into the Case Report Form according to the study protocol requirements. At the end of the study, the investigator will submit the Case Report Forms for all patients enrolled in this study to the data management center. These Case Report Forms must be complete and signed. The consistency of the collected Case Report Form data will be checked. Data queries will be issued for inconsistent data, requiring clarification by the physician.

VII. Statistical Analysis

1. Statistical Software

The data statistical work will be completed by a biostatistician using the statistical software SPSS 22.0.

2. Data Description

Measurement data will be expressed as mean \pm standard deviation ($\bar{x} \pm s$), using normality tests and t-tests. Enumeration data will be expressed as n (%), using the Chi-square test (χ^2 test). A P-value < 0.05 will be considered statistically significant.

3. Data Statistics

All hypothesis tests will be two-sided, and a P-value < 0.05 will be considered statistically significant. Baseline data will be evaluated for comparability between groups, using two-tailed statistical tests at the $\alpha=5\%$ level. Group comparisons for enumeration data will use the Chi-square test, and group comparisons for measurement data will use the t-test.

4. Statistical Analysis Plan

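### PaO2 is compared between arms with no record of inspired oxygen and no stated sampling time or oxygen condition, so any difference in oxygen given would be mixed with the lung effect

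*Combined protocol and SAP*

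**What the plan says.** The background closes with the aim "to evaluate whether bronchoscopic treatment can alleviate dysphagia symptoms, improve hypoxia, pulmonary infection, and SAP prognosis". The secondary objectives in section II list "arterial partial pressure of oxygen (PaO_2" among the outcomes to be compared between the two groups. No other oxygenation outcome is named. Oxygen saturation appears in section 5.3 only as a monitoring limit during the procedure.

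For the analysis, section VII.3 says that "group comparisons for measurement data will use the t-test". It names no covariate, neither baseline value nor oxygen given.

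Supplemental oxygen is mentioned once, in the bronchoscopy steps of section 5.3: "Under continuous nasal cannula oxygen and vital sign monitoring via ECG". Only the observation group has that procedure, one or two times. Care in the other arm is described as follows: "The control group will receive conventional anti-infective and expectorant therapy, plus suction via suction catheter as needed". Oxygen therapy outside the procedure is not described for either arm.

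Section 1.1 requires that "Pneumonia occurs within 72 hours after stroke, confirmed by chest imaging examination", and no criterion in 1.1 or 1.2 concerns oxygen need or room-air status. Section 4.2 sets a 7-day observation period but no day for a blood gas. Section 5.2, although its title includes blinding, describes assignment only.

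**The concern.** PaO2 depends on the oxygen a patient is breathing as well as on how well the lungs transfer it. A value on its own can be read as lung function only if the inspired oxygen is known, or is the same for everyone. This plan secures neither.

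Randomisation does not help here, because oxygen is set after assignment and can respond to the patient's condition, by staff who are not said to be blinded. The distortion could go either way. If control patients who do worse were given more oxygen, their PaO2 would be raised and a real benefit hidden. If bronchoscopy patients were on more oxygen when sampled, a benefit could appear with no change in the lungs.

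At stake is the conclusion on hypoxia. Without oxygen recorded at each gas, nobody could tell afterwards whether the comparison was fair, and no later adjustment would be possible.

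**Working it through.** **The plan's own figure.** There is none to reproduce. The documents give no SD, expected difference or power for PaO2. What follows shows only how sensitive the planned test would be to a shift of a given size.

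**Inputs from the documents.** 60 patients in total (III.2); t-test, two-sided, P<0.05 (VII.3).

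**Assumed inputs.** Equal split, 30 per arm (group sizes are not stated). SD of PaO2 of 10, 15 or 20 mmHg. An oxygen-driven difference in mean PaO2 of 5 mmHg, with no lung effect.

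**Step 1: chance of P<0.05 with no lung effect.** The noncentrality is shift / (SD × √(2/30)), where √(2/30) = 0.2582. With 58 degrees of freedom the two-sided critical value is 2.002. Probabilities come from the noncentral t distribution.

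| SD (mmHg) | Noncentrality for a 5 mmHg shift | Chance of P<0.05 |
|---|---|---|
| 10 | 5 / 2.582 = 1.94 | 48% |
| 15 | 5 / 3.873 = 1.29 | 25% |
| 20 | 5 / 5.164 = 0.97 | 16% |

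With no shift the figure is 5%.

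**Step 2: the opposite direction.** Suppose a true benefit of 10 mmHg, opposed by a 5 mmHg oxygen shift. The net difference is 5 mmHg. Power for the full 10 mmHg would be 97%, 72% and 48% at SD 10, 15 and 20. With the opposing shift it falls to the 48%, 25% and 16% of Step 1.

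**Step 3: how large an oxygen gap gives 5 mmHg?** As an assumed gas model, take PaO2 = r × (713 × FiO2 − 50), where 713 = 760 − 47, 50 = 40/0.8, and r (the share of alveolar PO2 reaching arterial blood) is 0.5 to 0.7. Each 0.01 of FiO2 then moves PaO2 by r × 7.13, which is 3.6 to 5.0 mmHg. A mean FiO2 gap of 5 / 5.0 to 5 / 3.6 hundredths, about 0.010 to 0.014, gives 5 mmHg. Under this model a small gap is enough.

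**Step 4: does PaO2/FiO2 solve it?** Under the same model the ratio is r × (713 − 50/FiO2). Move FiO2 from 0.21 to 0.25 with the lungs unchanged:

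- Raw PaO2 goes from r × 99.7 to r × 128.3, a rise of about 29%.
- The ratio goes from r × 474.9 to r × 513.0, a rise of about 8%.

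The ratio removes most of the dependence on inspired oxygen, but not all of it.

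**The case against.** The strongest reply is that a difference in oxygen at sampling is inferred. The one documented use of oxygen is during bronchoscopy, once or twice, in one arm. No section says that a blood gas is drawn then, or that either arm receives oxygen as treatment. The background describes non-severe patients and section 1.1 requires stable vital signs, so many may need none. This stands. A reader might infer from section 5.3 that the observation group will be sampled on more oxygen and that the PaO2 result will be biased in its favour. The documents do not support that.

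A reader might also reach for larger figures. By the alveolar gas equation, an FiO2 difference of 0.04 moves alveolar PO2 by 0.04 × 713 = 28.5 mmHg. If a quarter of that (about 7 mmHg) reached the between-arm mean, the t-test would reject in about 76%, 43% and 27% of trials at SD 10, 15 and 20. But the quarter is not derived from anything, and 28.5 mmHg is an alveolar figure, not an arterial one. If it means that a quarter of one arm is shifted by the full amount, the within-arm spread widens too, and simulated rejection falls to about 53%, 34% and 23%. These figures should not be taken as the size of the problem.

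It can also be said that missing FiO2 is only part of an outcome left undefined, since no sampling day or baseline gas is stated either. That is right, and the fix has to cover it. Sampling under one common oxygen condition would be another valid design. Whether that is acceptable is a clinical question for the investigators and is not taken up here.

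CPIS and APACHE II are also secondary outcomes, but the plan does not list their components, so it does not show that either supplies an oxygen-adjusted measure.

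**Conclusion.** The point holds as a gap in how a secondary outcome is defined and recorded. The plan tests an aim about hypoxia with PaO2 and an unadjusted t-test, and it does not state the oxygen given or the time and condition of sampling. If oxygen differs between arms at sampling, the result is confounded in a direction nobody could establish.

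Whether it will differ is unknown. The 16% to 48% chance of a spurious significant result rests on an assumed 5 mmHg shift, assumed SDs of 20 down to 10 mmHg and an assumed 30 per arm. It illustrates sensitivity and does not predict a false-positive rate.

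A reader might conclude that the trial's main result is in doubt. It is not on this ground: the primary objective concerns dysphagia and pneumonia, and PaO2 is one item in an unranked secondary list. This is a cheap improvement that should be made.

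**What to change.** - Fix the blood-gas times: one at baseline and one at the end of the 7-day observation period. The documents schedule neither at present.
- At each gas, record on the CRF the FiO2, or the cannula flow and device. State in advance one conversion from flow to FiO2.
- Make end-of-period PaO2/FiO2 the oxygenation outcome. Compare it between arms by a linear model with baseline PaO2/FiO2 as covariate.
- Report raw PaO2 and the oxygen given, by arm, as supportive results, so that readers can see whether the arms were sampled under similar conditions.

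The cost is a few CRF fields, a short addition to section VII.3, and two scheduled gases per patient if these are not already routine. There are two limits. FiO2 estimated from cannula flow is approximate and adds noise. The ratio lessens the dependence on inspired oxygen without removing it (about 8% against 29% in the example above), which is why oxygen given should be shown by arm as well.

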1.1 Inclusion Criteria

- Meets the diagnostic criteria for acute stroke and is clearly diagnosed through head MRI or CT examination.
- According to the Wada drinking water test, there is indeed difficulty swallowing.
- Pneumonia occurs within 72 hours after stroke, confirmed by chest imaging examination, and meets the diagnostic criteria for stroke-related pneumonia.
- Clear consciousness, stable vital signs, and able to cooperate with bronchial examination.

1.2 Exclusion Criteria

- The condition is critical, with severe hemiplegia and mental disorders that cannot tolerate bronchoscopy treatment.
- Combined lung tumors, open pulmonary tuberculosis, coagulation dysfunction, severe cardiovascular and cerebrovascular diseases, severe heart, liver, and kidney dysfunction, and pulmonary infection before stroke.
- Not willing to undergo bronchoscopy examination.

- Individuals with previous esophageal functional structural abnormalities.
- Disagree with participating researchers.

4.1 Study Implementation Period: September 2019 --- September 2021

4.2 Study Observation Period: Observation for 7 days starting from enrollment.

5. Study Execution

This is a single-center, prospective, randomized, controlled, clinical study.

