5.1 Enrollment

Before the study begins, the investigator must clearly and verbally explain the study's circumstances, potential risks, and benefits to the patient or their authorized representative. The patient or their authorized representative and the investigator must sign and date the informed consent form. The patient can only enter the screening process and subsequently participate in the study after signing the informed consent form.

After signing the written informed consent, the patient will be assessed to determine if they meet the study criteria:

1. Patient's medical history;
2. Vital signs;

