5.4 Adverse Events

Record adverse events, the number of and reasons for trial dropouts in detail.

IV. Adverse Events

1. Classification of Adverse Events and Serious Adverse Events

Common adverse reactions during bronchoscopy include: laryngospasm, airway bleeding, pneumothorax, cardiac arrest, aspiration, hoarseness.

Medical Device Adverse Event: Any harmful event unrelated to the intended effect of a medical device that occurs during the normal use of an approved, qualified medical device, leading or potentially leading to human injury.

Among these, **death** and **serious injury events** must be reported to the monitoring agency. Serious injury refers to any of the following:

- ① Life-threatening;
- ② Resulting in permanent impairment of a body function or permanent damage to a body structure;
- ③ Necessitating medical or surgical intervention to prevent such permanent impairment or damage.

Subject Death: An event resulting in the death of a subject.

Life-Threatening: An event which, in the investigator's judgment, places the subject at immediate risk of death without medical intervention. It does not include an event that might have caused death had it occurred in a more severe form.

Hospitalization: An event resulting in admission to the hospital, regardless of length of stay. This does not include emergency room observation or outpatient clinic visits.

Prolongation of Hospitalization: An event that results in or prolongs a subject's hospitalization.

Persistent or Significant Disability/Incapacity: An event resulting in a condition that substantially disrupts the subject's ability to conduct normal life functions. This does not include relatively minor symptoms such as headache, nausea, vomiting, diarrhea, influenza, or accidental injury.

Important Medical Event: An event that may not be immediately life-threatening or result in death or hospitalization but, based on appropriate medical judgment, may jeopardize the subject and may require medical or surgical intervention to prevent one of the outcomes listed above (e.g., subject death, life-threatening, hospitalization, prolongation of hospitalization, congenital anomaly, or persistent disability/incapacity).

2. Severity

Physicians can use the following definitions to judge the severity of all adverse events and serious adverse events, serving as study endpoints/data cut-off points.

[Mild] The adverse event is transient, and the patient tolerates it easily.

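### Observation closes 7 days after enrolment, no later than the 1-week treatment ends, so no safety follow-up is planned after treatment and a late bronchoscopy gets little

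*Combined protocol and SAP*

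**What the plan says.** Section III.4.2 defines one observation period: "Observation for 7 days starting from enrollment". No other follow-up period is stated for patients who complete the trial.

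Section III.5.3 says "Both groups will receive continuous treatment for 1 week". The observation group has, in addition, "bronchoscopic treatment 1-2 times", with no day and no interval fixed. Lavage fluid is cultured, and the operator is to "select sensitive antibiotics for instillation therapy based on the bacterial culture results of the airway secretions".

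Section III.5.1 puts consent and the eligibility check before participation: "The patient can only enter the screening process and subsequently participate in the study after signing the informed consent form".

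On safety:
- Section III.5.4 asks for adverse events to be recorded but gives no collection window.
- Section IV.1 lists the common reactions to bronchoscopy, among them aspiration, pneumothorax and airway bleeding. Its definitions relating to seriousness include permanent impairment, persistent or significant disability, and "Prolongation of Hospitalization: An event that results in or prolongs a subject's hospitalization".
- Section IV.3 sets a 24-hour reporting clock that starts when the physician learns of a serious event.
- Section III.1.3 requires follow-up of patients who withdraw because of an adverse event, for an unstated time.

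The paragraph just before Section II names clinical safety as an aim. Section II lists length of hospital stay as a secondary outcome.

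**The concern.** The observation clock starts at enrolment, not at the last procedure, and it runs for the same length as the treatment. A patient whose bronchoscopy falls late in the week therefore leaves observation soon afterwards, or at once. The documents say that bedside bronchoscopy has not been reported before for this use, so the trial's own safety data carry most of the weight.

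If Section III.4.2 is followed as written, harm that appears a few days after a late procedure could be missed. Only the observation group is exposed to that procedure, so any loss would fall on that group and could make bronchoscopy look safer than it is. Some of the plan's seriousness definitions also depend on what happens after day 7 in a patient who is still in hospital.

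**Working it through.** The plan gives no calculation to reproduce; this is timeline arithmetic.

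**Inputs**
- Observation: 7 days from enrolment (III.4.2). With enrolment as day 0, it ends on day 7.
- Treatment: 1 week, i.e. 7 days, in both groups (III.5.3).
- Lag L from enrolment to start of study treatment: L ≥ 0, since participation follows consent and screening (III.5.1). The documents give no value.
- Day d of a bronchoscopy: not stated (III.5.3).

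**Step 1: observation after the end of treatment.** Treatment ends on day L + 7, so the observation left is 7 − (L + 7) = −L days.
- L = 0: 0 days
- L = 1: −1 day
- L = 2: −2 days

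It is never positive.

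**Step 2: observation after a bronchoscopy on day d.** The maximum is 7 − d days.

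| Day of bronchoscopy | 0 | 1 | 2 | 3 | 4 | 5 | 6 | 7 |
|---|---|---|---|---|---|---|---|---|
| Days observed afterwards, at most | 7 | 6 | 5 | 4 | 3 | 2 | 1 | 0 |

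**Step 3: an illustration only.** Assume, without support in the documents, that procedure days are equally likely over days 0 to 7.
- One procedure: mean follow-up is (7+6+5+4+3+2+1+0)/8 = 28/8 = 3.5 days. Follow-up is 2 days or less for days 5, 6 and 7, i.e. 3/8 = 38%.
- Two procedures on different days: there are 28 pairs, and b of them have day b as the later day. Mean follow-up after the later one is the sum of b(7 − b) over b = 1 to 7, divided by 28: (6+10+12+12+10+6+0)/28 = 56/28 = 2.0 days. Follow-up is 2 days or less in (5+6+7)/28 = 18/28 = 64% of pairs.

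**Step 4: which definitions in IV.1 need later data.**
- Judgeable within the window: death, life-threatening events, significant disability, and intervention to prevent permanent damage.
- Not reliably established for a patient still in hospital at day 7: prolonged hospitalisation (needs the discharge date), permanent impairment or damage, and the persistent limb of the disability definition.

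**Step 5: other text that might fill the gap.** III.1.3 covers only patients who withdraw for an adverse event. III.5.4 has no end date. IV.3 says how fast to report a known event, not how long to look for one. Length of stay (II) needs tracking to discharge, but of a date and not of events; for anyone in hospital past day 7 it also conflicts with III.4.2. None of these plans safety follow-up for patients who complete the week.

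**The case against.** The strongest reply is that the documents never say adverse-event collection closes on day 7. III.5.4 and IV.3 have no end date, III.1.3 requires some follow-up, and length of stay implies contact to discharge. A site could reasonably go on recording. This stands in part: the event window is undefined rather than expressly closed. But III.4.2 is the only period stated, and a site that follows it stops at day 7.

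Four stronger readings are tempting, and the documents do not support them.

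- *That the seriousness criteria cannot be judged at all.* Most can (Step 4). Only permanence, persistence and prolonged stay are affected.
- *That culture results force a second bronchoscopy late in the week.* III.5.3 ties the choice of instilled antibiotic to the culture, but does not say that a second procedure waits for it. No turnaround time is given, and a single early procedure satisfies the plan. How often late procedures would occur is unknown.
- *That the loss does favour bronchoscopy.* This needs delayed procedural harm that occurs and goes unrecorded. The list in IV.1 concerns reactions during the procedure, and no latency is given. Both groups share the same window. The bias is possible, not shown.
- *That a fixed window such as day 10 follows from adding 72 hours to 7 days.* The 72 hours come from the inclusion criterion "Pneumonia occurs within 72 hours after stroke". That is an eligibility limit after stroke, not a latency for procedural complications.

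It is also fair to say that safety is absent from the listed objectives in Section II and that Section VII plans no specific safety comparison. The effect on the stated efficacy comparisons is therefore small.

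**Conclusion.** The point holds in a limited form. As written, the plan has no observation after treatment ends, and follow-up after a bronchoscopy on day d is at most 7 − d days, ranging from 7 down to 0. Delayed harm after a late procedure could go unrecorded. If it did, the loss would be on the bronchoscopy side only.

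The first conclusion assumes that the treatment week is counted from trial entry. The 7 − d limit needs only III.4.2. The share of patients affected cannot be derived, because procedure days are not stated; the figures in Step 3 are illustrations. The efficacy assessments at day 7 are not called into question, except that length of stay needs data beyond that day for patients still in hospital.

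**What to change.** Keep day 7 for the efficacy assessments, and make these changes:

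1. Amend III.4.2 and III.5.4 so that adverse events, serious adverse events and deaths are collected in both groups from randomisation to hospital discharge. Use the inpatient record that length of stay already requires. The existing 7 days remain the minimum for anyone discharged sooner.
2. Report events still open at discharge with their status at that time. Discharge will not always settle permanence, so the status should be stated as such.
3. Record the date and time of each bronchoscopy on the CRF, so that time from the last procedure can be reported.
4. Reconcile the length-of-stay outcome (II), the withdrawal follow-up (III.1.3), the observation period (III.4.2), the treatment week (III.5.3) and the safety definitions (IV.1). Any fixed window beyond discharge is for the sponsor to set.

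The cost is protocol wording, a few CRF fields and some extra data collection. The one statistical drawback is that collection time will differ between groups if lengths of stay differ. Report events both to day 7, where the windows are equal, and to discharge.
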